- u Fasting lipid profile: Patients should not eat or drink anything except water for 4-12 hours depending on weight and age as specified below. If a patient attends these visits in a nonfasting state, this will not be considered a protocol violation. Recommended fasting times by age and weight are as follows:
- Patients ≥ 12 years: fast for 12 hours prior to laboratory test
 - Patients 8 to < 12 years and weighing > 50 kg: fast for 12 hours prior to laboratory test
 - Patients 8 to < 12 years and weighing ≤ 50 kg: fast for 8 hours prior to laboratory test
 - Children < 8 years and weighing 25 to ≤ 50 kg: fast for 8 hours prior to laboratory test
 - Children < 8 years and weighing 10 to < 25 kg: fast for 6 hours prior to laboratory test
 - Children < 8 years and weighing < 10 kg: fast for 4 hours prior to laboratory test
- v Patients in the age cohort of age 2 to ≤ 7 years will not have flow cytometry testing due to blood volume limitations.
- w If patients are eligible for vaccination with tetanus, diphtheria, and pertussis (tDaP) and/or pneumococcal conjugate vaccine according to local recommended schedule of vaccination, IgG titers for eligible vaccine will be evaluated at prevaccination, 4 weeks post vaccination, and 12 weeks post vaccination.
- x Estradiol (for females) or testosterone (for males) will be collected for the assessment of pubertal development in patients aged 8 to < 18 years.
- y PK samples will be collected as described in Sections 9.5.2.

NOTE: Due to blood volume restrictions, some laboratory tests may not be collected. Laboratory samples are recommended to be collected as described in a sponsor-provided weight-based prioritization chart in [Appendix 6](#).

Table JAHV.2. Schedule of Activities

Visit #	Screening		Open-Label Lead-in Perioda					Double-Blind Randomized Withdrawal Period							Early Termination	Post-Treatment Follow-Up	
	V1	V1a	V5b baseline	V6	V7	V8	V9	V10	V11	V12	V13	V14	V15	V16			V17
Study Week			W0	W2	W4	W8	W12	W16	W20	W24	W28	W32	W36	W40	W44	ETVc	V801d
Study Day (Approximately)	-42 to -1		1e	14	28	56	84	112	140	168	196	224	252	280	308	Any Week	28 ± 5 Days after Last Dose
Visit Window (Days)				±3			±7										
Informed consent and assentf	X																
Complete medical history	X																
Immunization record	X		X	X	X	X	X	X	X	X	X	X	X	X	X		
Demographics	X																
Physical examinationg	X																
Tanner Staging in patients ≥8 years old (see Section 9.4.6.3)			X														

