10.3.3.2. Secondary Analyses

Secondary efficacy and health outcomes analyses ([Table JAHV.8](#)) will be based on the following study periods and study populations:

- OLLI period population: All participants who take at least 1 age-based final dose as confirmed by PK assessments of investigational product in the OLLI period, other than the Safety/PK population. Baseline is defined as Week 0.
- DBW period population: All randomized patients in DBW period following intent-to-treat (ITT) principles.

Table JAHV.8. Secondary Efficacy Endpoint Analyses

Endpoint	Population	Analysis Period	Treatment Comparisons	Analysis Method
Proportion of disease flare	DBW	Week 16 to Week 44	Baricitinib versus placebo	Logistic regression with NRI
PedACR core set variables: change from baseline	OLLI	Week 2 to Week 12	No comparison	Summary statistics
	DBW	Week 16 to Week 44	Baricitinib versus placebo	ANCOVA with LOCF
PedACR30/50/70/90/100 response rates (compare to patient's condition prior to first dose of investigational product)	OLLI	Week 2 to Week 12	No comparison	Summary statistics
	DBW	Week 16 to Week 44	Baricitinib versus placebo	Logistic regression with NRI
PhS and PsS scores (CHQ-PF50): change from baseline	OLLI	Week 2 to Week 12	No comparison	Summary statistics
	DBW	Week 16 to Week 44	Baricitinib versus placebo	ANCOVA with LOCF
Parental Impact –Time/Emotion scores (CHQ-PF50): change from baseline	OLLI	Week 2 to Week 12	No comparison	Summary statistics
	DBW	Week 16 to Week 44	Baricitinib versus placebo	ANCOVA with LOCF
Inactive disease: proportion	OLLI	Week 2 to Week 12	No comparison	Summary statistics
	DBW	Week 16 to Week 44	Baricitinib versus placebo	Logistic regression with NRI
Minimal disease activity: proportion	OLLI	Week 2 to Week 12	No comparison	Summary statistics
	DBW	Week 16 to Week 44	Baricitinib versus placebo	Logistic regression with NRI
Remission: proportion	DBW	Week 28 to Week 44	Baricitinib versus placebo	Logistic regression with NRI
JADAS-27: change from baseline	OLLI	Week 2 to Week 12	No comparison	Summary statistics
	DBW	Week 16 to Week 44	Baricitinib versus placebo	ANCOVA with LOCF
Pain severity VAS (CHAQ): change from baseline	OLLI	Week 2 to Week 12	No comparison	Summary statistics
	DBW	Week 16 to Week 44	Baricitinib versus placebo	ANCOVA with LOCF

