6.3.2. Non-Responder Imputation (NRI)

A non-responder imputation (NRI) imputation method can be justified based on the composite strategy (ICH E9R1) for handling intercurrent events. In this strategy a patient is defined as a responder only if (i) they meet the clinical requirements for response at the predefined time and (ii) they remain on the assigned study treatment. Failing either criteria by definition makes them a non-responder.

Binary efficacy and health outcome variables will be imputed using NRI after applying the censoring rule to those who discontinued study drug. Patients will be considered a non-responder for the NRI analysis if they do not meet the clinical response criteria or are entirely missing the visit at the analysis time point. Randomized patients without at least 1 postbaseline observation will also be defined as non-responders for the NRI analysis.

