
Inactive disease
	
Inactive disease is indicated by the presence of all of the following (Wallace et al. 2011):
 
 No joints with active arthritis based on JADAS-27 No fever, rash, serositis, splenomegaly, hepatomegaly, or generalized lymphadenopathy attributable to JIA as assessed by the investigator No active uveitis as assessed by the investigator Normal erythrocyte (ESR) or hsCRP (ie, within normal limits in the local laboratory or, if elevated, not attributable to JIA) Physician's Global Assessment of Disease Activity indicating no active disease (best possible score on scale [0]) Duration of morning stiffness less than 15 minutes In inactive disease analysis as secondary endpoint, ESR measure is used as acute-phase reactant measure. 	
Proportion of patients who achieved inactive disease
	
 Step 1: If joint with active arthritis isn't 0, stop; else Step 2: If there is fever, rash, serositis, splenomegaly, hepatomegaly, or generalized lymphadenopathy attributable, stop; else Step 3: If uveitis, stop; else Step 4: If ESR>20, stop; else Step 5: If physician's global assessment of disease activity isn't 0, stop; else Step 6: If stiffness >15min, stop; else Step 7: Conclude the patient achieved inactive disease status. 	
Missing if any component is missing. NRI will be applied to missing data.

Secondary Efficacy Endpoint Analyses

Measure	Description	Variable	Derivation/Comment	Imputation Approach if with Missing Components
Minimal disease activity	Minimal disease activity is calculated based on the scores from the Physician's Global Assessment of Disease Activity, Parent's Global Assessment of Patient's overall Well-Being, and the number of swollen joints as described in Consolaro et al. 2012.	Proportion of patients who achieved minimal disease activity	
 • if physician's global assessment of disease activity ≤ 3.5, and • if parent's global rating of patient's overall well-being ≤ 2.5, and • if swollen joint count ≤ 1, then conclude the patient reaches minimal disease activity; all else conclude the minimal disease activity is not reached. 	
Component is missing if baseline or postbaseline value is missing. LOCF will be applied for post baseline missing values.
 
If all components are missing after LOCF, NRI will be applied to missing data.

Secondary Efficacy Endpoint Analyses

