Measure	Description	Variable	Derivation/Comment	Imputation Approach if with Missing Components
Disease remission	Remission is defined as inactive disease for at least 24 consecutive weeks (Wallace et al. 2011). In inactive disease as secondary endpoint, ESR measure is used as acute-phase reactant in the core criteria. Thus, the disease remission as secondary endpoint is based on ESR.	Proportion of patients who achieved minimal disease activity	
 At Visit 13, check if there are inactive disease status in all Visit 7, Visit 8, Visit 9, Visit 10, Visit 11, Visit 12, if yes, conclude the patient has achieved disease remission status. At Visit 14, check if there are inactive disease status at Visit 8, Visit 9, Visit 10, Visit 11, Visit 12, Visit 13, if yes, conclude the patient has achieved disease remission status. At Visit 15, check if there are inactive disease status at Visit 9, Visit 10, Visit 11, Visit 12, Visit 13, Visit 14, if yes, conclude the patient has achieved disease remission status. At Visit 16, check if there are inactive disease status at Visit 10, Visit 11, Visit 12, Visit 13, Visit 14, Visit 15, if yes, conclude the patient has achieved disease remission status. At Visit 17, check if there are inactive disease status at Visit 11, Visit 12, Visit 13, Visit 14, Visit 15, Visit 16, if yes, conclude the patient has achieved disease remission status. 	Missing if item is missing. NRI will be applied to missing data.

Secondary Efficacy Endpoint Analyses

Measure	Description	Variable	Derivation/Comment	Imputation Approach if with Missing Components

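### The printed remission rules cover 20 scheduled weeks and skip the visit being classified, so they do not test the 24-week definition

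*SAP*

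**What the plan says.** In the disease remission row of SAP Table JAHV.6.4 (Section 6.10.2) the description reads: "Remission is defined as inactive disease for at least 24 consecutive weeks". Protocol 9.1.2.3 sets the same duration. The derivation column of that row then gives five rules, one each for Visits 13, 14, 15, 16 and 17. Each lists the six earlier visits and concludes remission if all six are inactive; for the last: "At Visit 17, check if there are inactive disease status at Visit 11, Visit 12, Visit 13, Visit 14, Visit 15, Visit 16". The classified visit is in none of the five lists. The supplementary hsCRP version follows the same logic (Table JAHV.6.6).

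Protocol Table JAHV.8 plans the remission comparison, by logistic regression between arms, for "Week 28 to Week 44", that is, Visits 13 to 17. SAP 6.3.2 counts a patient as a responder only if "they meet the clinical requirements for response at the predefined time" and the patient remains on assigned treatment.

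The inactive-disease row, on which remission depends, has "Step 4: If ESR>20, stop; else" in its derivation, while its description accepts a value that is, "if elevated, not attributable to JIA". Its imputation cell reads: "Missing if any component is missing. NRI will be applied to missing data".

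The JADAS-27 row of the same table gives normalised ESR as (ESR − 20)/10, labelled 0 to 10, and a total score range of 0 to 57.

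**The concern.** The definition and the rules in one table row disagree, and no separate algorithm document is cited for remission as it is for flare and PedACR response. The printed rules are therefore what a programmer would code. Someone working from the definition and someone working from the rules would produce different remission rates.

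The patients at issue were inactive at six consecutive visits, attended the next one on treatment, and were not classed inactive there. They may have active joints, a non-zero physician global score or an ESR above 20. As printed they are reported in remission at a visit where they fail the SAP's own inactive-disease criteria. Nothing printed would stop a patient inactive at Visits 11 to 16 who flares at Visit 17 from being both a primary-endpoint event and a remission at Week 44.

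Remission is a between-arm secondary endpoint. The primary analysis and the sample size do not depend on it, and the SAP applies no multiplicity control.

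**Working it through.** **Inputs.** Scheduled days from Protocol Table JAHV.2: V7 = 28, V8 = 56, V9 = 84, V10 = 112, V11 = 140, V12 = 168, V13 = 196, V14 = 224, V15 = 252, V16 = 280, V17 = 308. The widest visit window is ±7 days. Required duration: 24 × 7 = 168 days.

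**Span of each set** = day of last visit − day of first visit.

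| Classified visit | Printed set | Printed span | Set with classified visit added | Span |
|---|---|---|---|---|
| 13 (Week 28) | 7–12 | 168 − 28 = 140 | 7–13 | 196 − 28 = 168 |
| 14 (Week 32) | 8–13 | 196 − 56 = 140 | 8–14 | 224 − 56 = 168 |
| 15 (Week 36) | 9–14 | 224 − 84 = 140 | 9–15 | 252 − 84 = 168 |
| 16 (Week 40) | 10–15 | 252 − 112 = 140 | 10–16 | 280 − 112 = 168 |
| 17 (Week 44) | 11–16 | 280 − 140 = 140 | 11–17 | 308 − 140 = 168 |

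Every printed set spans 140/7 = 20 weeks. Windows cannot close the gap: 140 + 7 + 7 = 154 days = 22 weeks. The seven-visit sets span exactly 24 scheduled weeks, and the earliest, Weeks 4 to 28, agrees with the protocol's first remission time point.

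**Direction.** Each seven-visit set contains the printed six-visit set, so anyone meeting the seven-visit rule also meets the printed one. With visit statuses held fixed, the printed rule can only add patients.

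**Size.** Let q be the probability that a patient classed inactive at six consecutive visits, who attends the next on treatment, is still classed inactive there. The documents do not give q; the values below are assumed.

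| q | Share of printed-rule remissions failing at the classified visit, 1 − q | Relative inflation, 1/q − 1 |
|---|---|---|
| 0.95 | 5% | 5.3% |
| 0.90 | 10% | 11.1% |
| 0.85 | 15% | 17.6% |
| 0.80 | 20% | 25.0% |

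**JADAS-27.** The stated maximum is 10 (physician) + 10 (scaled parent) + 27 (joints) + 10 (normalised ESR) = 57, so the stated range holds only if normalised ESR stays within 0 to 10. The printed formula does not ensure this: ESR 0 gives (0 − 20)/10 = −2.0, and ESR 140 gives (140 − 20)/10 = 12. In the hsCRP version, hsCRP 0 gives (0 − 10)/10 = −1.0. Randomisation includes a stratum with ESR not elevated, so ESR values below 20, which score negative as printed, are to be expected.

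**The case against.** Six checks can be read as standing for six 4-week intervals: for Visit 13, the first check is at Week 4, 24 weeks earlier. That requires the last checked status to hold until the classified visit. The SAP does not say so, and inactive disease is itself assessed at that visit.

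SAP 6.3.2 may be held to supply the missing current-visit condition for every binary endpoint, so that the rules are incomplete rather than wrong. But the remission criteria as printed never refer to the classified visit. Non-responder imputation therefore has no failure to act on when the patient attends on treatment with complete data. At best the two sections need reconciling.

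The remission row has its own missing-data instruction, which can be read to cover the classified visit. On that reading a patient with a missing component there is already a non-responder. That one example is open to interpretation; observed active disease or a raised ESR is not.

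The error also does not carry forward. A patient not inactive at Visit 13, 14, 15 or 16 fails the next visit's rule, because that visit is then in the checked set. Visit 17 has no later check.

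The numbers may be small. If 5% to 20% of 64 patients per arm met the printed rule (assumed), that is 3.2 to 12.8 patients; with 1 − q of 5% to 20%, about 0.2 to 2.6 per arm per visit would be affected. This limits the importance of the point but does not remove the contradiction.

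Finally, the stated 0 to 10 range can be read as an implied limit on the JADAS-27 term. That makes it a clarification, but one that should be written into the formula.

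**Conclusion.** The concern holds. All five printed rules fall 4 scheduled weeks short of the definition and omit the classified visit, and visit windows cannot make up the difference. Relative to the 24-week rule applied to the same visit statuses, the printed rule overstates remission by 1/q − 1: 5% to 25% for an assumed q of 0.95 to 0.80.

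Measured against the written definition rather than the derived statuses, the net error has no fixed sign. Step 4 has no exception for an ESR elevation unrelated to JIA, and a missing component makes the patient not inactive; both work the other way. No direction is claimed for the difference between arms, because q may differ by arm and no remission rate is given. The effect of the JADAS-27 formula on the arm difference cannot be computed, because no ESR or hsCRP distribution is given.

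The point should be fixed, but it is confined to secondary and supplementary endpoints.

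**What to change.** - **Remission.** At each of Visits 13 to 17, require inactive disease at that visit and at the six preceding scheduled visits (7–13, 8–14, 9–15, 10–16, 11–17). Apply the same rule to the hsCRP version.
- **Windows.** State that scheduled visits attended within their windows count as 24 weeks. With ±7 days at each end the actual dates can span 168 − 14 = 154 to 168 + 14 = 182 days (22 to 26 weeks), so this is a convention and should be declared.
- **Inactive disease.** State whether Step 4 or the attribution exception in the description governs.
- **JADAS-27.** Write the limits into the formulas: NormESR = min(10, max(0, (ESR − 20)/10)) and Norm hsCRP = min(10, max(0, (hsCRP − 10)/10)).
- **Clerical, to be checked against the source tables first.** The remission row's variable label names minimal disease activity, and hsCRP remission appears with a Week 16 entry.

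The cost is SAP wording and a few lines of derivation code, with no new data. The downside is that the reported remission rate may be slightly lower.

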Abbreviations: ANCOVA = analysis of covariance; CHAQ = Childhood Health Assessment Questionnaire; CHQ-PF50 = Child Health Questionnaire-Parent Form 50; DBW = DBW = double-blind withdrawal; hsCRP = high-sensitivity C-reactive protein; JADAS = Juvenile Arthritis Disease Activity Score; MMRM = mixed model repeated measures; OLLI = open-label lead-in; PedACR = Pediatric American College of Rheumatology; VAS = Visual Analog Scale.

6.10.3. More Supplementary Analysis

For the composite measures/endpoints which have acute-phase reactant ESR or CRP as component, in general, the ESR version of derivation will be used as the main version of derivation for the first and secondary analysis. The hsCRP version of derivation will be used as a supplementary version for the supplementary analysis and will be provided for selected visits only, as defined in [Table JAHV.6.6](#) and [Table JAHV.6.7](#).

Table JAHV.6.6. Description of the Use of ESR and hsCRP in Endpoints Derivation

Endpoint	Version	Calculation difference between ESR version and hsCRP version	Measure	Type of the endpoint	Analysis
flare	ESR version	Derivation refer to Table JAHV.6.4	time to flare	primary endpoint	primary analysis
	ESR version	Derivation refer to Table JAHV.6.4	proportion of patients who have disease flare	secondary endpoint	secondary analysis
PedACR response	ESR version	Derivation refer to Table JAHV.6.4	proportion of patients who achieve PedACR response	secondary endpoint	secondary analysis
	PedACR (hsCRP) response	Derivation logic is same as ESR version	proportion of patients who achieve PedACR-hsCRP response	supplementary	supplementary analysis
JADAS-27	ESR version	Derivation refer to Table JAHV.6.4	change from baseline of JADAS-27	secondary endpoint	secondary analysis
	hsCRP version	Derivation logic is same as ESR version, use Norm hsCRP=(hsCRP-10)/10 instead of NormESR	change from baseline of JADAS-hsCRP-27	supplementary	supplementary analysis
inactive disease	ESR version	Derivation refer to Table JAHV.6.4	proportion of patients who achieve inactive disease status	secondary endpoint	secondary analysis
	hsCRP version	Derivation logic is same as ESR version, use hsCRP>3 instead of ESR>20	proportion of patients who achieve inactive disease status (hsCRP)	supplementary	supplementary analysis
disease remission	ESR version	Derivation refer to Table JAHV.6.4	proportion of patients who achieve disease remission status	secondary endpoint	secondary analysis
	hsCRP version	Derivation logic is same as ESR version, use hsCRP>3 instead of ESR>20	proportion of patients who achieve disease remission status (hsCRP)	supplementary	supplementary analysis

Abbreviations: ESR = erythrocyte sedimentation rate; hsCRP = high-sensitivity C-reactive protein; JADAS = Juvenile Arthritis Disease Activity Score; PedACR = Pediatric American College of Rheumatology.

Table JAHV.6.7. Description hsCRP Related Supplementary Analysis

Measure	Variable	Population	Analysis Time Point	Treatment Comparisons	Analysis Method	Analysis Type
PedACR-hsCRP response	PedACR-hsCRP 30/50/70/90/100 response rates (compare to patient's condition prior to first dose of investigational product)	OLLI2	Week 12	No comparison	Summary statistics	Supplementary analysis
		DBW	Week 16, week 32, Week 44	Baricitinib versus placebo	Logistic regression	Supplementary analysis
Inactive disease status (hsCRP)	Proportion of patients who achieved inactive disease status (hsCRP)	OLLI2	Week 12	No comparison	Summary statistics	Supplementary analysis
		DBW	Week 16, Week 32, Week 44	Baricitinib versus placebo	Logistic regression	Supplementary analysis
Disease remission status (hsCRP)	Proportion of patients who achieved disease remission status (hsCRP)	DBW	Week 16, Week 32, Week 44	Baricitinib versus placebo	Logistic regression	Supplementary analysis
		OLLI2	Week 12	No comparison	Summary statistics	Supplementary analysis
JADAS-hsCRP-27	Change from baseline of JADAS-hsCRP-27 score	DBW	Week 16, Week 32, Week 44	Baricitinib versus placebo	ANCOVA	Supplementary analysis
		OLLI2	Week 12	Baricitinib versus placebo	MMRM	Supplementary analysis

Abbreviations: DBW = double-blind withdrawal ; hsCRP = high-sensitivity C-reactive protein; JADAS = Juvenile Arthritis Disease Activity Score; OLLI = open-label lead-in; PedACR = Pediatric American College of Rheumatology.

6.11. Planned Exploratory Analyses

In consideration of the limited sample size in JIA categories (polyarticular and extended oligoarticular [combined] versus ERA and JPsA [combined]), a non-stratified logrank test may be applied to analysis of time to flare as an exploratory analysis. The p-value and median time to flare (if applicable) by treatment group will be reported. Treatment comparisons may also be analyzed using a Cox proportional hazards model. The hazard ratio with 95% CIs will be reported. The Kaplan-Meier product limit method will be used to estimate the survival curves for time-to flare. Time-to flare will also be summarized graphically by treatment group using Kaplan-Meier techniques.

6.11.1. X-ray and Structure Data

Semiannual wrist, hand, finger, and knee radiographs to monitor bone age and long bone growth. Imaging will be required until skeletal maturity is attained, and this should be determined by a qualified physician at the site. For patients already enrolled at the time of protocol amendment (d), the x-ray procedures will be optional. For patients that consent to the x-ray procedures, x-rays must be completed within 30 days from time of consent/assent and every 6 months \pm 30 days thereafter.

Descriptive statistics will be used to summarize the modified total Sharp score (mTSS) (when data are available), skeletal age, and chronological age at baseline for all the patients who have a baseline value available.

For patients in the DBW period, an analysis of covariance model with baseline mTSS, presence of erosion at baseline (yes or no), and treatment group in the model will test the treatment difference between baricitinib and placebo in change from baseline to Week 44 in mTSS when data are available. Linear extrapolation will be applied for patients who are missing the radiograph at Week 44 but who have baseline and postbaseline radiographs available.

The skeletal age can deviate from the chronological age calculated from the date of birth. Results will include a description of the skeletal age, the chronological age, and the difference between skeletal age and chronological age at baseline and post baseline when data are available.

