- c Early termination visit (ETV) occurs if the patient does not have a PedACR30 response rate at Week 12, experiences a flare during the double-blind withdrawal (DBW) (and are not moving to the open-label extension), or terminates participation early. If the ET occurs on the same day as the scheduled visit, any assessments/procedures conducted during the scheduled visit should not be repeated for a separate ETV.
- d Patients who complete the study or discontinue early from the study will have a post-treatment safety follow-up visit (V801) approximately 28 days after the last dose of investigational product. This applies only to patients who do not enter the Open-Label Extension Study.
- e This is the first day of taking the investigational product. .
- f The parent or legal guardian will sign the informed consent form (ICF) and the patient will sign the assent form (as applicable) per local requirements prior to any study assessments, examinations, or procedures being performed.
- g One complete physical examination (excluding pelvic and rectal examinations) will be performed at Visit 1. All subsequent physical examinations may be symptom-directed. A complete physical examination may be repeated at the investigator's discretion at any time. Must include an assessment of serositis, splenomegaly, hepatomegaly, or generalized lymphadenopathy attributable to JIA.
- h Semiannual wrist, hand, finger, and knee radiographs to monitor bone age and long bone growth. Imaging will be required until skeletal maturity is attained, and this should be determined by a qualified physician at the site. For patients already enrolled in JAHV at the time of this amendment, the x-ray procedures will be optional. For these ongoing patients that consent to the x-ray procedures, x-rays must be completed within 30 days from time of consent/assent and every 6 months \pm 30 days thereafter.
- i All patients with active uveitis must be excluded at screening. Signs and symptoms of active uveitis should be monitored. Patients with ERA and JPsA may have a higher risk of active uveitis so mandatory evaluation is required at W12 (V9), W44 (V17), ETV, and V801.
- j Study drug should not be dispensed before review of the Trial Manager report.
- k Patients will return all investigational products for drug accountability.
- l Patient-reported questionnaires will be administered via an on-site eCOA device or paper and is recommended to be completed prior to any clinical examinations.

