4.3. Exploratory Objectives

Table JAHV.4.3. Exploratory Objectives and Endpoints

[figure not shown]
Objectives	Endpoints

Exploratory
 
 • To evaluate the quality of life (QOL) in children with JIA treated with baricitinib • To evaluate the QOL in children with JIA treated with baricitinib compared to placebo • To evaluate the efficacy of baricitinib compared to placebo in structural joint damage • Describe the skeletal age in pediatric patients 	
 • Change in European Quality of Life-5 Dimensions–Youth version (EQ-5D-Y) scores during the OLLI period • Change from baseline in EQ-5D-Y scores during the DBW period • Change from baseline in the individual scales (Global Health; Physical Functioning; Role/Social Limitations-Physical; Role/Social Limitations-Emotional/Behavioral; Bodily Pain/Discomfort; Behavior; Global Behavior Item; Mental Health; Self-Esteem; General Health Perception; Change in Health; Parental-Impact-Time; Parental Impact-Emotion; Family-Activities; Family-Cohesion) as measured by the CHQ-PF50 • Change from the baseline (Week 0) to the end of the double-blind withdrawal (DBW) period of radiographic images of the hands/wrists using modified Total Sharp Score (mTSS [van der Heijde method]; van der Heijde 2000; Ravelli et al. 2007) • Change from baseline (Week 0) to the end of the DBW in skeletal age based on hand/wrist radiograph and chronological age.

Abbreviations: DBW = double-blind withdrawal; JIA = juvenile idiopathic arthritis; OLLI = open-label lead-in.

5. Study Design

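### For patients on the six-monthly film schedule, the Week 44 mTSS comparison would be extrapolated from a line that is nearly half open-label run-in

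*SAP*

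**What the plan says.** - **Objective.** SAP Table JAHV.4.3 lists an exploratory objective: "To evaluate the efficacy of baricitinib compared to placebo in structural joint damage". Its endpoint is "Change from the baseline (Week 0) to the end of the double-blind withdrawal (DBW) period of radiographic images of the hands/wrists", scored by mTSS.
- **Test.** SAP 6.11.1 specifies an ANCOVA with baseline mTSS, presence of erosion at baseline and treatment group, to "test the treatment difference between baricitinib and placebo in change from baseline to Week 44 in mTSS when data are available".
- **Missing films.** "Linear extrapolation will be applied for patients who are missing the radiograph at Week 44 but who have baseline and postbaseline radiographs available".
- **Film schedule.** Protocol Table JAHV.2, footnote h, and SAP 6.11.1 set "Semiannual wrist, hand, finger, and knee radiographs to monitor bone age and long bone growth". The purpose given is growth monitoring, not joint damage. A ±30-day window is stated. The protocol writes it for ongoing patients who consent after enrolment; the SAP's wording leaves out the word ongoing.
- **Who is filmed.** "For patients already enrolled at the time of protocol amendment (d), the x-ray procedures will be optional".
- **Treatment periods.** All patients take open-label baricitinib to Week 12. Responders are then randomised to baricitinib or placebo for up to 32 weeks, to Week 44. A patient who flares leaves the study (Protocol 5.1), and SAP 6.1.3 ends the DBW period at flare.

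**The concern.** The test is labelled Week 44, but the six-monthly schedule puts no nominal film there. For a patient on that schedule, the rule written for a missing film becomes the rule that supplies the outcome. The line it extends starts at Week 0 and crosses the run-in, when both arms receive the same drug. For placebo patients, treatment changes at Week 12, partway along the line. A blended slope is then projected over Weeks 26 to 44 and reported as a between-arm result with a p-value. A diluted difference could be read as absence of a structural effect at Week 44, a time at which most of the values might not have been observed.

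**Working it through.** **Inputs.** Week 44 is study day 308, visit window ±7 days (Protocol Table JAHV.2). Films are every 6 months, ±30 days where the window applies. The run-in is 12 weeks and the randomised period 32 weeks. Planned flare rates are 35% on baricitinib and 60% on placebo (SAP 5.2). The documents give no mTSS progression rate, effect size or power, so there is no planned mTSS figure to reproduce.

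The flare rates do reproduce the planned sample size. The hazard ratio is ln(0.65)/ln(0.40) = 0.470. Freedman's formula gives 61 events, and 61/0.475 = 128.4, against 128 planned. Schoenfeld's gives 56 events, 56/0.475 = 117.9, and 131.0 after dividing by 0.90 for dropout.

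**Step 1: film timing.** Six months is about 183 days.
- First post-baseline film: day 183 (153 to 213), or about Week 26 (21.8 to 30.4).
- Second film, counted from Week 0: day 365 (335 to 395). This is at least 335 − 315 = 20 days after the Week 44 visit window closes.
- If each interval instead runs from the previous film, two shortened intervals reach 2 × 152.6 = day 305, which is inside days 301 to 315.

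**Step 2: size of the distortion.** Let progression be r per week in the run-in (both arms), then b on baricitinib and p on placebo, each constant. With one post-baseline film at week T:
- True Week 44 difference = 32(p − b).
- Extrapolated difference = (44/T) × (T − 12) × (p − b).
- Ratio = 44(T − 12)/(32T). The run-in rate r cancels, so the Week 0 baseline alone does no harm; the extrapolation does.

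| Film week T | Extrapolated difference | Ratio to 32(p − b) | Understated by |
|---|---|---|---|
| 21.8 | 19.8(p − b) | 0.618 | 38% |
| 26 | 23.7(p − b) | 0.740 | 26% |
| 30.4 | 26.6(p − b) | 0.832 | 17% |
| 44 | 32(p − b) | 1.000 | 0% |

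**Step 3: sensitivity to the constant-rate assumption, T = 26.**
- Arms begin to separate 4 weeks after randomisation: (44/26) × 10/28 = 0.60. After 8 weeks: (44/26) × 6/24 = 0.42.
- Placebo excess decays at rate k per week: (44/26)(1 − e^(−14k))/(1 − e^(−32k)). For k = 0.0385 (half-life 18 weeks) this is about 1.00. For k = 0.1 (about 7 weeks) it is 1.33, an overstatement.
- Target is the end of DBW and the patient flares: the line credits 23.7 weeks of placebo, so it over-projects anyone who flares before Week 12 + 23.7 = 35.7. Placebo patients still unflared at Week 26 average 28.1 placebo weeks to flare or Week 44 at the planned rate, and 23.7/28.1 = 0.84.

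**Step 4: patients with no post-baseline film.** Assume constant hazards of −ln(0.65)/32 on baricitinib and −ln(0.40)/32 on placebo. The probability of flare in the 14 weeks from Week 12 to Week 26 is then 1 − 0.65^(14/32) = 17% and 1 − 0.40^(14/32) = 33%. Without an early-termination film, the extrapolation rule cannot reach these patients.

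**The case against.** A reader might infer that no film can exist near Week 44, that nearly every value will be extrapolated, and that the difference is understated by construction. The documents do not support any of these.

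- **Films near Week 44 cannot be ruled out.** In the text as read here, the film row of Table JAHV.2 marks no visit, not even baseline, although Table JAHV.1 marks a film at Visit 2. The row may be damaged, so a film at Visit 17 or early termination cannot be excluded. The SAP's own wording presupposes that some Week 44 films exist. Step 1 also shows that accumulating windows could put one there.
- **The number extrapolated is unknown.** The rule needs a baseline film. Films were optional for patients enrolled before amendment (d), and for those who agreed they were timed from consent, so some may have no Week 0 film and fall outside the rule.
- **The 17% to 38% range is conditional.** It carries a window that the protocol writes for ongoing patients over to a child filmed at Week 0.
- **The direction is conditional.** Step 3 shows that front-loaded damage can cancel or reverse the attenuation, and that stopping the target at flare can reverse it for individual patients.
- **The effect on the test is limited.** If all films share a common time, extrapolation multiplies every change by 44/T. The ANCOVA p-value is then the one for the observed change; only the estimate and its Week 44 label are affected. If p = b the distortion is zero, so the extrapolation does not inflate type I error.

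All of this stands, and the endpoint is exploratory with no power claim. What survives is that the rule, followed as written on the nominal schedule, labels a Week 26 observation as Week 44 and projects it with a slope that ignores the change of treatment at Week 12.

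**Conclusion.** The point holds in a conditional form. For a patient with a Week 0 film and the next near Week 26, the Week 44 value would be extrapolated from a line of which 12/26 = 46% is common run-in. Under constant progression within each period and continued assigned treatment, the Week 44 difference is understated by about 26%, or 17% to 38% if the ±30-day window applies. Delayed separation makes this worse; front-loaded damage could remove or reverse it.

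Two related gaps stand beside it. Early flarers may have no post-baseline film, about twice as often on placebo as on baricitinib at the planned rates. Table JAHV.4.3 also targets the end of the DBW period while 6.11.1 targets Week 44, and these differ for any patient who flares. The primary analysis is untouched.

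**What to change.** In SAP 6.11.1:
- Delete the linear extrapolation to Week 44.
- Analyse observed films taken after randomisation. Model change in mTSS on baseline mTSS, presence of erosion at baseline (already prespecified, so keep it), time since Week 0 with a common slope, and treatment × time since randomisation. Only post-Week 12 time then carries the treatment contrast.
- Report the contrast as exploratory and descriptive, at the observed film time, with the number of patients per arm who have a post-randomisation film.
- Align the endpoint in Table JAHV.4.3 with 6.11.1, so that one time point is stated and its meaning for patients who flare is clear.

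The cost is SAP wording and one changed model, with no additional films. Three limits remain: no Week 44 estimate is quoted, the model still assumes linear progression within each period, and the loss of early flarers is disclosed but not corrected.
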